Up to 3 repeat study treatments of the same dose volume may be given if criteria are met.

Enrollment should occur as soon as possible once it has been confirmed that the subject has met all inclusion criteria and has not met any exclusion criteria within 7 days of initial intubation. Treatment initiation is to begin within 6 hours of enrollment. If the subject does not tolerate one of the 40 ml quarter doses, the dosing for that dose may be terminated at that time. It is recommended that the other quarter doses remain 40 ml; however, a lower dose may be administered for the remaining aliquots at the Investigator's discretion.

Up to 3 retreatment doses are allowed no sooner than 6 hours apart (from completion of previous dose). Subjects are eligible for retreatments if they remain on MV, there is no evidence of pneumothorax, the P/F ratio is under 300 (or S/F ratio is under 315, if no arterial line is present), and there are no safety concerns that would prevent retreatment (in the opinion of the investigator). Retreatments are given at the discretion of the investigator.

Retreatment should be performed in the same manner as the initial treatment.

Early Discontinuation of Treatment:

The administration of study treatment may be discontinued at any time prior to the completion of dosing based on the clinical judgment of the PI. Reasons for discontinuation of study treatment include, but are not limited to the following:

- 1. An AE which places subject at risk occurs (eg, severe bradycardia, hypotension, cardiac arrest)
- 2. If, in the PI's best medical judgment, initiating or continuing the subject's exposure to study treatment is not in the best interest of the subject's safety.

Subjects whose treatment is discontinued based on the PI's judgment will continue in the study. Subjects whose treatment is discontinued based on the subject's request may continue in the study; however, if a subject withdraws consent, the subject will be withdrawn from the study and no further data collection will be done.

Study Duration:

Subject participation will be from enrollment to 30 days after enrollment unless they have an ongoing SAE (to be followed for an additional 30 days).

Overall, study enrollment will be completed in approximately 7 to 8 months, with the last subject last visit approximately 8 to 9 months from the time the first subject enrolled.

Statistical Analysis:

The statistical analysis will be based on all enrolled subjects.

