1.2 Schedule of Activities (SOA)

		Primary Phase Through Day 30		
Measurement/Procedure	Screening	Treatment Period (Day 1)	Post-Treatment Period (Days 2-5)	Final Period (Days 6 to 30)
Informed consent	X			
Inclusion/exclusion Criteria	X			
Demographics	X			
Medical history	X			
Physical examination	X			
Enrollment		X		
Study treatment administration		X		
Vital signs	X	X	X^2	X
ABG (PaO ₂ , PaCO ₂ , pH)		X^1	X	X
FiO ₂ , SpO ₂ , P _{aw} , EtCO ₂		X^1	X	X
Ventilator parameters (rate, peak and plateau pressure, lung compliance)		X^2	X^2	
Respiratory support parameters	X	X	X	X
Pressure volume loops		X^3		
AEs/SAEs		X	X	X ⁵
Concomitant medications	X	X	X	X
Final Visit/Discharge				X^4

Note: Day 1 for all subjects is the day of enrollment.

Time 0 (study treatment), 1, 2, 4, 8, 12, 18, 24 hours after treatment

 $^{^{2}}$ $\,$ Recorded every 12 hours at 08:00 and 20:00 through Day 5.

³ Recorded every 2 hours through 24 hours.

⁴ Occurs at Day 30, withdrawal from the study, or death (whichever occurs first).

⁵ AEs ongoing at Day 30 will be followed for an additional 30 days or until stop date/time (whichever occurs first).

TABLE OF CONTENTS

TITLE PAGE	I
STATEMENT OF COMPLIANCE	3
PROTOCOL AGREEMENT	4
1 PROTOCOL 02-CL-2001A	5
1.1 Summary	5
1.2 Schedule of Activities (SOA)	14
TABLE OF CONTENTS	15
2 INTRODUCTION	19
2.1 Study Rationale	19
2.2 Background	19

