7 STUDY INTERVENTION DISCONTINUATION AND PARTICIPANT DISCONTINUATION/WITHDRAWAL

7.1 Discontinuation of Study Intervention

Study treatment may be interrupted at any time as circumstances dictate (eg, peri-dosing event). In all cases, emergent care of the subject takes precedence over study treatment; however, it is important to complete SRT as soon as possible. If study treatment is interrupted or stopped, the reason for doing so must be recorded, especially in regard to peri-dosing events (bradycardia, desaturation, hypotension, pallor, gagging/regurgitation/vomiting).

Discontinuation from study treatment does not mean discontinuation from the study, and the remaining study procedures should be completed as indicated. If a clinically significant finding is identified after enrollment (including, but not limited to changes from baseline), the investigator or qualified designee will determine if any change in participant management is needed. Any new clinically relevant finding will be reported as an AE.

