7.2 Participant Discontinuation/Withdrawal from the Study

The subject is free to withdraw consent from subject participation in the study at any time. An investigator may discontinue or withdraw a participant from the study if any clinical AE or other medical condition or situation occurs such that continued participation in the study would not be in the best interest of the subject.

The reason for subject discontinuation or withdrawal from the study will be recorded on the end of study eCRF page. Subjects who are enrolled and subsequently withdraw, or are withdrawn or discontinued from the study, will not be replaced.

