8.4.4 Time Period and Frequency for Event Assessment and Follow-Up

The occurrence of an AE or SAE may come to the attention of study personnel during the study, or upon review by a study monitor.

All AEs including local and systemic reactions not meeting the criteria for SAEs will be captured on the appropriate eCRF. All AEs occurring while on study must be documented appropriately regardless of relationship. All AEs will be followed to adequate resolution.

Any medical condition that is present at the time that the participant is screened will be considered as baseline and not reported as an AE. However, if the study participant's condition deteriorates at any time during the study, it will be recorded as an AE.

Changes in the severity of an AE will be documented to allow an assessment of the duration of the event at each level of severity to be performed. AEs characterized as intermittent require documentation of onset and duration of each episode.

The site will record all reportable events with start dates occurring any time after informed consent is obtained until 7 days after the last day of study participation or Day 30 (whichever occurs first). Events will be followed for outcome information until resolution or stabilization, or for 30 days after study participation. When possible, information collection should continue for subjects that withdraw or discontinue treatment early.

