8.4.5 Adverse Event Reporting

All AEs are to be assessed in all subjects throughout Day 30 (from enrollment to study withdrawal or completion) and documented in the study eCRF. Each AE should be reported spontaneously or in response to general, non-directed discussion with the attending nurse or physician (eg, "has there been any change in subject status since the last assessment period?"). For each AE, the investigator should obtain all information required to complete the AE page of the eCRF, in accordance with eCRF completion guidelines (provided separately by Windtree).

All AEs, regardless of seriousness, severity, or relationship to study participation, must be recorded (using medical terminology) in the source document and on the AE page of the eCRF. Whenever possible, diagnoses should be given when signs and symptoms are due to a common etiology.

All AEs must be followed until resolution or until a stable clinical end-point is reached, or for at least 30 days after the subject's last day in the study if an AE is ongoing at the time the subject completes the study.

Documentation of AEs in the eCRF must include the following parameters; (1) duration (time of onset and resolution), (2) severity or grade, (3) outcome, (4) action taken, and (5) relationship to study drug. AEs will be coded using the Medical Dictionary for Regulatory Activities (MedDRA).

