### **3 STUDY SUBJECT CHARACTERISTICS**

#### **3.1 Subject Disposition**

Subject disposition will be summarized by treatment group using frequency and percent. The number of subjects screened, randomized and received study medication (modified intent-to-treat [mITT] population), received study medication regardless of randomization (safety population), and without protocol violations (per-protocol population) will be described. If more than 5% of subjects experience a treatment interruption, a population of subjects without interruptions will also be defined.

The number of subjects who completed the study or died will be summarized using frequency and percent by treatment group and overall. Reasons for early discontinuation from the study include withdrawal of consent and lost-to-follow up. A subject may withdraw consent (through their legally authorized guardian) at any time without prejudice to further care.

The number of subjects who discontinued treatment early will be summarized using frequency and percent by treatment group and overall. Reasons for early discontinuation of treatment include device failure or malfunction, AE or ADE during dosing, PI's best medical judgment, and respiratory deterioration during dosing.

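### After an investigator withdraws a subject from the study for an AE, the documents disagree on what is still collected, and none requires Day 30 vital status

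*Protocol*

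**What the plan says.** **Stopping treatment.** The Protocol separates this from leaving the study. Section 7.1: "Discontinuation from study treatment does not mean discontinuation from the study, and the remaining study procedures should be completed as indicated". The synopsis agrees: "Subjects whose treatment is discontinued based on the PI's judgment will continue in the study".

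**Leaving the study.** Section 7.2 adds a second route: "An investigator may discontinue or withdraw a participant from the study if any clinical AE or other medical condition or situation occurs". The sentence goes on to require that continued participation would not be in the subject's best interest. The reason goes on the end-of-study eCRF, and withdrawn subjects are not replaced.

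**Collection after leaving.**
- Schedule of Activities, footnote 4, on the final visit: "Occurs at Day 30, withdrawal from the study, or death (whichever occurs first".
- Protocol 8.4.5: "All AEs are to be assessed in all subjects throughout Day 30 (from enrollment to study withdrawal or completion"). The same section has AEs that are still open followed after the subject's last day in the study.
- Protocol 8.4.4 records onsets up to 7 days after the last day of participation, capped at Day 30, and follows recorded events for outcome. It adds: "When possible, information collection should continue for subjects that withdraw or discontinue treatment early".
- Protocol 8.2.5 reports deaths through discharge and Day 30 and does not mention withdrawn subjects.
- SAP 1.2.2 ends efficacy follow-up at completion or withdrawal. All-cause mortality is one of the secondary efficacy endpoints.
- For withdrawn consent only, the synopsis says: "if a subject withdraws consent, the subject will be withdrawn from the study and no further data collection will be done".

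**Analysis.** SAP 4.3 uses available data without imputation. SAP 3.1: "Reasons for early discontinuation from the study include withdrawal of consent and lost-to-follow up".

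**The concern.** Safety and tolerability is a primary endpoint, and all-cause mortality is both a safety and a secondary efficacy endpoint. Treatment is a short bolus course, so most of the 30 days is observation. Withdrawal under 7.2 for an AE depends by definition on the subject doing badly. If follow-up then lapses, the outcomes at risk are deaths, new SAEs and air leaks later in the month, in subjects likely to be at higher risk than those who remain. With 30 subjects planned in the Protocol and 20 in the SAP, one or two unrecorded deaths would visibly move the mortality figure, and a summary of available data would not reveal it.

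**Working it through.** **1. The follow-up rules side by side, for a subject withdrawn by the investigator on Day 2 with consent still in place**

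| Source | What it implies after Day 2 |
|---|---|
| Schedule, footnote 4 | Final visit is Day 2 |
| Protocol 8.4.5 | No assessment of new AEs; open AEs still followed |
| SAP 1.2.2 | Efficacy follow-up, which includes mortality, ends |
| Protocol 8.4.4 | New onsets recorded to Day 2 + 7 = Day 9; recorded events followed for outcome; anything further only where feasible |
| Protocol 8.2.5 | Death reported to Day 30; withdrawn subjects not addressed |
| Synopsis | Its stop on collection does not apply, because consent was not withdrawn |

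Under 8.4.5 the window for new events closes on Day 2. Under 8.4.4 it closes on Day 9, leaving Days 10 to 30, which is 21 days, to best effort. Section 8.2.5 could be read as covering death, but footnote 4 and SAP 1.2.2 point the other way. No section makes Day 30 vital status mandatory for this subject.

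**2. Size, as illustration only**

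There is no stated figure to reproduce: the study has no hypothesis and no formal sample size calculation, and no withdrawal rate is given.

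Inputs from the documents: N = 30 (Protocol 9.2) or 20 (SAP 2.2.3). For mortality, 14% and 24% in the arms of the earlier lucinactant ARDS study (Protocol 2.4.1), and as high as 40% in ARDS (Protocol 2.2.1).

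Assumption: k subjects are withdrawn for an AE, and all k die afterwards unrecorded. This is the worst case. With D true deaths, rounded to whole subjects, the available-data estimate is (D − k)/(N − k).

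| True mortality | k = 1 | k = 2 | k = 3 |
|---|---|---|---|
| 4/30 = 13.3% | 3/29 = 10.3% | 2/28 = 7.1% | 1/27 = 3.7% |
| 7/30 = 23.3% | 6/29 = 20.7% | 5/28 = 17.9% | 4/27 = 14.8% |
| 12/30 = 40.0% | 11/29 = 37.9% | 10/28 = 35.7% | 9/27 = 33.3% |
| 5/20 = 25.0% | 4/19 = 21.1% | 3/18 = 16.7% | 2/17 = 11.8% |

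At N = 30 the shortfall runs from 40.0 − 37.9 = 2.1 points to 13.3 − 3.7 = 9.6 points. If withdrawn subjects stay in the denominator and count as alive, the estimate is (D − k)/N, which is slightly lower still: for 7/30 it gives 20.0%, 16.7% and 13.3%.

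The direction depends on who is withdrawn. If two withdrawn subjects both survived, the available-data figure would be 7/28 = 25.0% against a true 23.3%. The bias is downward only when withdrawn subjects die more often than those who remain, which is the likelier case when an AE prompted the withdrawal.

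**3. How likely is at least one such withdrawal?**

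With assumed rates p of 2%, 5% and 10%, 1 − (1 − p)^N gives 46%, 79% and 96% at N = 30, and 33%, 64% and 88% at N = 20. These show only that a low rate would be enough for the gap to matter. They do not estimate the rate.

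**The case against.** The strongest reply is that the Protocol keeps far more follow-up than a quick reading of 7.2 suggests, and much of this stands.

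- A reader might infer that collection simply stops at withdrawal. It does not. The only explicit stop is tied to withdrawn consent, 8.4.4 and 8.4.5 both follow existing events beyond participation, and 8.2.5 has deaths reported to Day 30 without a stated exception.
- A reader might infer that everyone who tolerates the drug badly is at risk of being lost. The synopsis and 7.1 keep subjects in the study when only treatment is stopped. Only formal study withdrawal is at issue, and it carries a best-interest condition.
- A reader might take the 44 of 110 subjects (40%) with an SAE in the earlier ARDS studies and conclude that about 0.40 × 30 = 12 subjects could be lost. The documents do not support that as an expected loss. It ignores the best-interest condition, SAEs include deaths that are already recorded, and those studies used a lavage procedure that the Protocol describes as more invasive.
- A subject withdrawn because of an SAE already counts in overall SAE incidence. What could be missed are later SAEs and deaths.
- SAP 3.1 introduces its reasons as examples, so it does not rule out an investigator decision, and the eCRF captures the reason.
- The 8.4.4 sentence on continued collection can be squared with the synopsis by treating collection as not possible once consent is gone.

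What the reply does not do is supply a rule. A seven-day extension and a best-effort request do not secure Day 30 status. Following recorded events does not capture new ones. The general statement on deaths sits beside a footnote that makes withdrawal the final visit.

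**Conclusion.** The point holds as an inconsistency with a possible informative loss. For investigator withdrawal with consent intact, footnote 4, the assessment window in Protocol 8.4.5 and SAP 1.2.2 end follow-up at withdrawal. Protocol 8.4.4 and 8.2.5 extend it in part, and Day 30 vital status is not guaranteed. In a trial this small, one to three unrecorded deaths among withdrawn subjects would lower reported mortality by about 2 to 10 percentage points at N = 30. That rests on three assumptions: such withdrawals occur, the subjects die afterwards, and the deaths are not captured. The documents give no rate for any of these, so the figures show sensitivity and are not a forecast. The sponsor should correct this because safety is a primary endpoint and the remedy is mainly wording.

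**What to change.** **Protocol.** Reconcile 7.2, footnote 4 of the Schedule of Activities, 8.2.5, 8.4.4 and 8.4.5. State that after investigator withdrawal, Day 30 vital status and AE/SAE collection continue, by contact or record review, unless the subject withdraws consent. Limit the 8.4.4 sentence on continued collection to subjects who have not withdrawn consent. Leave the investigator's best-interest discretion over study procedures as it is. Reserving study withdrawal for withdrawn consent alone would remove a safeguard and is not needed to close the gap.

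**SAP.** Align 1.2.2 with the revised Protocol. In 3.1 and Table 1.2, add a category for investigator decision, with the reason. Report Day 30 mortality with the number of subjects of unknown vital status and an upper bound counting unknowns as deaths. With 5 recorded deaths and 2 unknown among 30, for example, the bound is (5 + 2)/30 = 23.3%, against an available-data figure of 5/28 = 17.9%.

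**Cost.** Wording changes in both documents, one disposition category, one extra line in the mortality table, and a contact or record check for the few subjects withdrawn. The Day 30 contact in Protocol 7.3 is written for discharged subjects, so it does not already cover this.

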7.3 Lost to Follow-Up

All efforts should be undertaken to ensure that no subject is lost to follow-up. It is expected that subjects will remain in the study site until the end of study; however, if a subject is discharged prior to the final evaluation, the subject should be contacted for the Day 30 visit. If the subject cannot be reached, at least 3 additional attempts must be made (at least one contact using telephone and at least one using email). If the subject still cannot be reached, a certified letter should be sent to the subject. If contact cannot be re-established after the certified letter, the subject will be considered lost to follow-up.

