5 STUDY POPULATION

5.1 Inclusion Criteria

Each subject must meet all inclusion criteria to be enrolled in this study:

- 1. Signed and dated ICF by the subject or legally authorized representative;
- 2. Age 18-75 (inclusive);
- 3. Assay positive for SARS-CoV-2 virus, preferably by polymerase chain reaction (PCR);
- 4. Endotracheal intubation and MV, within 7 days of initial intubation;
- 5. In-dwelling arterial line;
- 6. P/F ratio < 300;
- 7. Mean blood pressure \geq 65 mmHg, with or without vasopressor support, immediately before enrollment;
- 8. Bilateral infiltrates seen on frontal chest radiograph.

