8.2.5 Readmissions and death

Readmissions and death will be reported through discharge and Day 30. Hospitalization will be defined as any unplanned hospitalization (including admission to a hospital or any attendance in an acute care setting e.g. ED, or in another health care facility) of 24 hours or greater, regardless of whether the patient was admitted to the hospital.

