#### **4.3 Missing Data**

Missing values represent a potential source of bias in a clinical trial. Hence, every effort will be undertaken to fulfill all the requirements of the protocol concerning the collection and management of data; however, some missing data is inevitable. No imputation, including last observation carried forward, will be done for the any parameters; only available data will be considered. Any missing data or data anomalies will be communicated to the site(s) for clarification/resolution.

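### The lost-to-follow-up rule names no contact beyond the subject and no vital-status check, so a death after discharge or transfer can go unrecorded and Day 30 mortality may be understated

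*Protocol*

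**What the plan says.** Protocol 7.3 opens with a general duty, "All efforts should be undertaken to ensure that no subject is lost to follow-up", and an expectation, "It is expected that subjects will remain in the study site until the end of study". For anyone discharged before the final evaluation, the site contacts the subject for the Day 30 visit. If that fails, it makes at least three more attempts, with at least one by telephone and one by email. Then "a certified letter should be sent to the subject", and finally "If contact cannot be re-established after the certified letter, the subject will be considered lost to follow-up". The section names no relative, representative, hospital or death register.

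Other provisions bear on this:

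- **Consent.** Protocol 5.1, criterion 1: "Signed and dated ICF by the subject or legally authorized representative". All subjects are intubated at enrollment, so a second contact person will often be known to the site.
- **Death reporting.** Protocol 8.2.5: "Readmissions and death will be reported through discharge and Day 30". It names no source of information after discharge.
- **Endpoint.** Protocol 1.1 and the SAP Executive Summary list all-cause mortality under both secondary efficacy and safety.
- **Analysis.** SAP 4.2.2 reports deaths as frequency and percent without stating a denominator for subjects of unknown status. SAP 4.3 rules out imputation: "only available data will be considered".
- **Final visit.** Protocol 1.2 (footnote 4) places it at Day 30, withdrawal or death, and the footnote in SAP 2.2.4 agrees. The SAP Executive Summary, under Study Duration, places it at Day 30 or at discharge or transfer, if earlier.

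**The concern.** A subject who has died cannot answer a telephone call, an email or a letter. Among deaths that the site does not hear of otherwise, non-response is caused by the outcome being measured. A site can carry out every step that 7.3 spells out, record the subject as lost, and leave Day 30 vital status missing for a reason tied to death itself.

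The SAP has nothing to catch this. It plans no count of unknown vital status and no sensitivity analysis, and it does not say whether a lost subject stays in the denominator. With 20 to 30 subjects and no control arm, the mortality percentage is one of the main safety results, and one or two unknowns move it visibly. Ventilator-free days, which SAP 4.2.2 calls mortality adjusted, depend on vital status as well.

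**Working it through.** The documents give no figure to reproduce: no Day 30 mortality assumption, no expected loss rate and no formal sample size calculation. Simple bounds are the suitable check.

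**Inputs**

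- N = 30 (Protocol 9.2, up to 30) or 20 (SAP 2.2.3). The documents differ, so both are shown.
- L = number with unknown Day 30 vital status. Not in the documents; assumed 1 to 3, and it may be 0.
- x = deaths among those L, anywhere from 0 to L.
- d = recorded deaths.
- Illustrative mortality levels: 24% (one lucinactant group of KL4-ARDS-04 at Day 28, Protocol 2.4.1) and 40% (upper figure for ARDS, Protocol 2.2.1). At N = 30 these are 0.24 × 30 = 7.2, taken as 7 deaths, and 0.40 × 30 = 12 deaths.

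**Formulas**

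- True mortality = (d + x)/N.
- Lost counted as alive: reported = d/N, error = −x/N. The error is never upward and is at most L/N in size.
- Lost dropped: reported = d/(N − L). This is too low only if x/L > d/(N − L), that is, if the lost died at a higher rate than those observed. Otherwise it is equal or too high.

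**Direction of error: N = 30, 7 true deaths (7/30 = 23.3%), L = 2**

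| Deaths among the 2 lost | Recorded deaths | Counted as alive | Dropped |
|---|---|---|---|
| 2 | 5 | 5/30 = 16.7% | 5/28 = 17.9% |
| 1 | 6 | 6/30 = 20.0% | 6/28 = 21.4% |
| 0 | 7 | 7/30 = 23.3% (no error) | 7/28 = 25.0% (too high) |

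With 12 true deaths (40.0%) and L = 3, dropping the lost gives 9/27 = 33.3% if all three died and 12/27 = 44.4% if none did.

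**Width of the uncertainty, L/N**

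| L | N = 30 | N = 20 |
|---|---|---|
| 1 | 3.3 points | 5 points |
| 2 | 6.7 points | 10 points |
| 3 | 10.0 points | 15 points |

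**What a reader of the results would face.** With 7 recorded deaths and 2 unknown of 30, mortality is 7/30 = 23.3% if both are counted as alive, 7/28 = 25.0% if excluded, and 9/30 = 30.0% if counted as dead. With 5 recorded deaths and 2 unknown of 20, the figures are 25.0%, 5/18 = 27.8% and 7/20 = 35.0%. The planned tables would show one of the first two, and the plan does not say which.

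**The case against.** The steps in 7.3 can fairly be read as a minimum. The section asks for all efforts, sets three further attempts as a floor, and nothing in it bars a call to the representative who signed the consent. Protocol 8.2.5 requires deaths to be reported through Day 30, death is a serious adverse event (8.4.2), and 8.4.5 collects adverse events through Day 30. A death that the site learns of by any route is therefore recorded as a death. Subjects are also expected to stay at the site, so few or none may be lost. SAP 3.1 and Tables 1.2 and 1.3 would report loss to follow-up, from which a reader could form rough bounds.

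Much of this stands, and it rules out three stronger readings that a reader might infer:

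- **That deaths after discharge are lost as a matter of rule.** The documents do not say this. What is missing is a method of finding out, and only deaths the site never hears of are affected.
- **That the bias always runs toward lower mortality.** The working shows otherwise: two lost survivors who are dropped raise 23.3% to 25.0%.
- **That ventilation in another hospital distorts mortality.** It affects ventilator-free, ICU and hospital days. That gap comes mainly from Protocol 8.2.3, which captures respiratory support only to discharge, and from the SAP's final visit at discharge or transfer. It exists even when contact succeeds.

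The objection does not close the gap. The duty to report deaths names no source, and the one procedure for reaching discharged subjects works only for people able to reply. The expectation of remaining at the site carries no figure, while days in hospital is an endpoint and the SAP provides for discharge and transfer. A count of subjects lost is also not a count of unknown vital status: under the SAP's Study Duration text, a subject could have a final visit at discharge and never be pursued to Day 30.

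**Conclusion.** The point holds as a gap in ascertainment. A site that follows the stated sequence can leave Day 30 vital status missing in a way that depends on death, and the SAP has no rule for such subjects. Day 30 mortality may be understated; the documents do not establish that it will be.

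The size is bounded by L/N: 3.3 points per lost subject at N = 30 and 5 points at N = 20. The full amount applies only if every lost subject died and all are counted as alive. If none died, counting them as alive gives no error and dropping them gives an overstatement. If nobody is lost, there is no effect. L is an assumption throughout.

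These bounds should not be set against the 24% and 14% mortality figures from the earlier ARDS study as though they were a treatment difference. Those figures compare groups and are described as not statistically significant, whereas this trial has no comparator and no hypothesis.

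**What to change.** **Protocol 7.3.** Before a subject may be called lost, require contact with the legally authorized representative or next of kin and with the discharging or receiving hospital, and a check of public death records where local law allows. Assign lost only if Day 30 vital status is still unknown. Record the alternate contact at consent.

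**SAP 4.2.2 and 4.3.** State the mortality denominator. Report the number with unknown Day 30 vital status. Show mortality with these subjects counted as alive, excluded, and counted as dead.

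**Final visit.** Reconcile the Study Duration text in the SAP Executive Summary with Protocol 1.2 and SAP 2.2.4, so that follow-up to Day 30 clearly applies to discharged and transferred subjects.

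**Cost.** Protocol and SAP wording, one contact field, a few calls and a few added summary lines. No extra patients or clinical procedures. Reported mortality may be slightly less favourable. Vital status not sought at the time may be unrecoverable later.
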